Multiple trials of each activity may be conducted to ensure usable images have been acquired to complete the study. Radiation time will be kept as low as reasonably achievable (ALARA) and will not exceed two minutes. The RT will start the fluoroscope just prior to the subject beginning the activity trial and will stop the fluoroscope immediately after the subject completes each activity trial to ensure that the subject is not exposed during idol periods. On-time will be recorded on the subject's IC, as well as any output the fluoroscopy unit is able to provide.

In addition to fluoroscopy video, subjects will be videotaped from the shoulders down (to maintain subject anonymity) while performing the activities (live feed perspective). The speed level of each trial will be based on the comfort level of the subject. One of the researchers will be ready and in close proximity to assist each subject in case the participant requires help. This precaution will be practiced for all participants, regardless of physical wellbeing, age or prior results; no assumptions will be made as to any participant's capabilities. The participant will be allowed to rest as necessary and be instructed to stop the activity at the first sign of pain.

The fluoroscopic and video footage for the study activities will be stored on digital video files on a secure computer workstation and stored securely by UT researchers. It will then be uploaded onto the secure CMR database by these researchers. Once the data has been uploaded, identifiers are removed from the data automatically by the database, and a study and subject-specific identifier will be assigned to each subject.

JointVue three-dimensional ultrasound

Since the skeletal geometry is different for every person, computer aided design (CAD) models of the femur and tibia will be created for each specific subject. In order to create these CAD models, each subject will be asked to undergo a three-dimensional (3D) ultrasound using the JointVue proprietary software to reconstruct 3D femoral and tibial bones (Figure 2). A representative from JointVue will be present during data collection to conduct the ultrasound procedure in order to create the CAD models. This individual will sign a statement of confidentiality.

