Study data will then be uploaded onto a secure server that University of Tennessee researchers will use to conduct the kinematic analysis using a model-fitting approach, the relative pose of knee implant components will be determined in 3D from a single-perspective fluoroscopic image by manipulating a CAD model in 3D space.

Using a model-fitting technique, the 3D bones will be overlaid onto the fluoroscopic images to determine amount of medial OA offloading. Successive fluoroscopic images of each subject's stance phase, with and without the OA brace, will be downloaded to a computer. Images will be captured at five instances during stance-phase of gait: heel strike, 33% of stance phase, mid-stance, 66% of stance-phase and at toe-off. A comparative analysis will be conducted for each subject while wearing the OA brace and with their non-braced test. Then, the amount of medial condylar separation will be assessed for each subject.

[figure not shown]

Figure 2. Example of 3D bone creation.

CT Scan

Participants will be asked to schedule a CT scan at Porter Adventist Hospital at their convenience within 1 month of the initial data collection day. To ensure subject safety, CT will be limited to the affected knee and the rest of patient's body will be protected from radiation with lead protection. The CT scan will be limited to the study knee and will image 6 inches distal on the tibia and 6 inches proximal on the femur.

Private Health Information/Medical Record Data

It is not anticipated that the subjects' medical files should need to be accessed for any PHI for the study for recruitment or for the conduct of the study itself. However, contact information from patient files will be acquired for inquiring as to whether or not patients would be willing to participate. The only subject-specific data that will be necessary will be measurements of medial condyle separation from the medial tibial plateau for each subject with and without a brace. Researchers will acquire the measurements with the brace while they are conducting the data collection. Researchers may also acquire the subjects' medial condyle separation without the brace while they are present for data collection. However, if this is not possible or time does not permit, Colorado Joint Replacement staff may send that information to UT researchers via secure transfer (e.g., UT Vault).

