The subject data – fluoroscopy frames, video footage and ultrasound– will be uploaded and stored on CMR's secure server for use in this and future studies (if participant permission is obtained via IC) by the researcher(s) who attend data collection or appointed by [name]. Once data has been uploaded, the database automatically removes subject identifiers and assigns an ID for each subject. Only these files of de-identified data are now available for researchers to review and analyze. Only [name], [name] and [name] have access to the 5-Breg OA Brace Effectiveness V1.1 protocol

identifiable data that was originally uploaded by the GRA, as it remains in a password-protected portion of the secure server. Only [name] and [name] can grant access to this identifiable password-protected portion of the database by changing a user's level of authentication with different privilege levels.

Researchers would like to retain this study data in our secure database so as to continue to add relevant, current data to our digital collection to help us work with manufacturers in the future to create better orthopaedic products. Participants will be asked if their study data may remain a part of the CMR data collection for use in future studies in the IC. Likewise, should a subject choose to withdraw from the study, s/he will have the option as to whether or not data collected from them at the point of withdrawal may be used for data analysis or if their information should be destroyed from CMR records; subjects choosing to withdraw will be asked to complete a Revocation of Consent wherein they may indicate their preference regarding the data collected from them.

On the day of data collection, the list of patient names will be given to UT researchers and the researchers will generate subject-specific identifiers for each participant. A table will be generated for this study, indicating the participant's name and generated ID number; this table with subject names and corresponding ID numbers will be provided to Colorado Joint Replacement staff, so the staff will be aware of which identifier is linked with each subject. If necessary (i.e., time not permitting during data collection; researchers unable to collect measurement), Colorado Joint Replacement staff may relate the measurements of medial condyle separation from the medial tibial plateau for each subject without a brace securely to UT researchers via the UT Vault <https://vault.utk.edu/>.

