In vivo Three-Dimensional Determination of OA Brace Effectiveness

[name], PhD¹

¹University of Tennessee

Knoxville, TN

July 11, 2019

Send Correspondence To:

[name]
University of Tennessee
[name],
[name]
[contact]
[contact]
Email: [contact]

DATA ANALYSIS

Once the subjects have completed the activity, the fluoroscopic videos will be stored digitally and specific frames of interest will be captured from the video and exported into the preprocessing software.

Our 3D to 2D registration technique will be used to overlay the 3D models of the bones on their projection in the 2D fluoroscopic image. The fluoroscopic video would be digitized into frames and corrected for distortion. From here, the distortion-free images would be used with the 3D to 2D registration technique to extract *in vivo* patient femorotibial kinematics, which involves overlaying the 3D models of the components on their projection in the 2D fluoroscopic image.

Statistical analysis of the data will be carried out to analyze the two cohorts. All variables will be denoted as continuous. The data will be first checked for normality using the Shapiro-Wilk test. Only when the data is found to be normally distributed will parametric tests be used; otherwise, non-parametric tests will be used. The data will also be tested for equality of variance using the Barlett's test and Levene's test. The final selection criterion for the type of test to conduct will be based on the check for normality, as well as the check for equal variance. Therefore, for all the continuous variables, the following tests will be used:

1. Student's t-test (when the data is normally distributed and has equal variance).
2. Welch Anova test (when the data is normally distributed but has unequal variance).
3. Wilcoxon Mann Whitney U-test (when the data is not normally distributed).

All statistical tests will be carried out at 95% confidence level ($\alpha=0.05$) and will be performed using JMP® Statistical DiscoveryTM (SAS Institute Inc., Cary, NC) software.

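### The plan specifies no masking of brace condition, no random processing order and no trial-selection rule for the model fitting that yields medial separation, and it lets the two conditions be measured by different routes

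*Protocol*

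**What the plan says.** **Outcome.** Protocol, Private Health Information/Medical Record Data: "The only subject-specific data that will be necessary will be measurements of medial condyle separation from the medial tibial plateau", with and without a brace.

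**How it is obtained.** Protocol, JointVue three-dimensional ultrasound: "the 3D bones will be overlaid onto the fluoroscopic images to determine amount of medial OA offloading". The pose is found from a single-plane image "by manipulating a CAD model in 3D space". SAP, Data Analysis: "Our 3D to 2D registration technique will be used to overlay the 3D models of the bones on their projection in the 2D fluoroscopic image".

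**Comparison.** Protocol, same section: "A comparative analysis will be conducted for each subject while wearing the OA brace and with their non-braced test".

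**Trials and frames.** Protocol, Fluoroscopy: "Multiple trials of each activity may be conducted to ensure usable images have been acquired". The protocol fixes five points in stance, from heel strike to toe-off. The SAP says only that "specific frames of interest will be captured from the video and exported into the preprocessing software".

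**Nearest safeguard.** After upload the database strips subject identifiers and assigns an ID; then "Only these files of de-identified data are now available for researchers to review and analyze". The Computer Database section adds that student analysts cannot reach subject-specific information. Neither statement mentions brace condition.

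**Other measurement routes.** Private Health Information/Medical Record Data says researchers obtain the braced measurements during data collection. It allows clinic staff to send the unbraced measurement if it cannot be taken that day, without saying how clinic staff would measure it.

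**The concern.** The study question is directional: does the brace open the medial compartment? The answer rests on a gap read from a bone model placed on a single-plane image. If the person placing the model, or choosing the trial, knows that a frame is braced and expects a larger gap, a small consistent lean in the fit cannot be told apart from a brace effect.

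Two features of the plan add to this. The unbraced walk always comes first (Protocol, Fluoroscopy), so someone working in acquisition order could fit the braced frame already knowing that subject's unbraced result. And if a braced value came from the research team and an unbraced value from the clinic, the contrast would also carry any difference between measurers or methods.

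At stake is the interpretation of the main result: a positive finding could not be attributed to the brace alone.

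**Working it through.** The documents give no figure to reproduce here: no power calculation, SD, expected effect, registration error or repeatability figure.

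**Step 1. What is fixed and what is open**

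| Step | Fixed by the documents | Left open |
|---|---|---|
| Choice of trial | Several trials allowed until images are usable | Which usable trial is analysed, and who decides |
| Choice of frame | Five points in stance | Who identifies the frame, and whether condition is known |
| Fitting | Bone model overlaid on the 2D frame | Degree of operator input, processing order, sight of the paired result, masking |
| Coding | Subject identifiers removed, ID assigned | Any coding of brace condition |
| Source of the value | Researchers on the day; clinic staff possibly for unbraced | Whether both conditions must come from the same method |

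**Step 2. Effect of a systematic fitting difference**

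Let Δ be the true mean difference (braced minus unbraced), β the mean amount by which fitting enlarges the gap in braced frames, and e random error with mean zero. For subject i, observed difference = true difference + β + e, so the mean observed difference estimates Δ + β. A constant β shifts the mean and leaves the shape and spread unchanged. The SAP's normality check, variance checks and location tests therefore cannot reveal it.

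**Step 3. Illustration of size**

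Inputs: n = 20 analysed, 24 enrolled (Protocol, opening section); α = 0.05 (SAP, Data Analysis). Assumptions: two-sided test, paired t-test, Δ = 0, and b = β divided by the SD of the within-subject differences. The documents give no value for b, so a range is shown.

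The test statistic follows a noncentral t distribution with n − 1 degrees of freedom and noncentrality b√n. The false-positive rate is the probability that it falls outside ± the 97.5% point of the central t.

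| b | b√20 | n = 20 (19 df) | n = 24 (23 df) |
|---|---|---|---|
| 0 | 0 | 5.0% | 5.0% |
| 0.1 | 0.447 | 7.1% | 7.6% |
| 0.25 | 1.118 | 18.6% | 21.7% |
| 0.5 | 2.236 | 56.5% | 65.0% |

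Adding subjects makes this worse: the bias stays while the standard error shrinks.

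**Step 4. Dependence on the test**

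The SAP lists unpaired tests for two cohorts, not a paired test. For an unpaired t-test with 20 values per condition treated as independent (38 df, noncentrality b√(20/2), b now in per-condition SDs), the rates are 6.1%, 12.0% and 33.8% at b = 0.1, 0.25 and 0.5. The unit differs: SD of differences = per-condition SD × √(2(1 − ρ)), so the two scales agree only if the within-subject correlation ρ is 0.5. The documents do not give ρ.

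**The case against.** The strongest reply has five parts.

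- **Silence is not absence.** A reader might infer that fitting will be done unmasked. The documents do not say that; they only fail to specify masking. The protocol text that follows the Hard Copy heading was also not available to me. This stands, and the point is limited to what is specified.
- **Operator judgement is inferred.** No section says whether fitting is manual, semi-automated or automated. The phrase "by manipulating a CAD model in 3D space" ends a sentence about implant components, although this study models the subjects' own bones. This stands as a caution. A documented automated fit would answer much of the concern, but not the choice of trial or the alternative measurement routes.
- **Frames are not freely chosen.** The five stance points are fixed in advance. Correct; the remaining discretion is over which trial and the exact frame.
- **Brace hardware may unmask the frame.** The documents do not say whether hardware overlaps the joint. If it does, masking is partial, but selection by rule, random order and hiding the paired result still help.
- **The problem can be repaired.** A reader might infer permanent damage. Frames are stored and, with permission, kept indefinitely (Protocol, Computer Database), so masked refitting remains possible. This stands, although refitting repeats the work and depends on each subject's permission.

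It is also tempting to read the 57% as this trial's false-positive rate. It is not: it describes a paired t-test under an assumed bias, and nothing in the documents shows that any bias exists.

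**Conclusion.** The concern holds as a gap in the specification that can be closed cheaply, not as a demonstrated error. The plan leaves its one named, directional outcome without masking, random processing order or a trial-selection rule, and allows the two conditions to be measured by different routes with condition known. De-identification does not fill this gap, because it covers the subject only.

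The direction of the risk is clear: a tendency to fit wider gaps in braced frames adds one for one to the estimated effect. Its size is unknown. The 7% to 57% range rests on an assumed bias of 0.1 to 0.5 SD of the differences, a two-sided paired t-test, 20 subjects and no true effect. Confidence is medium, because the degree of operator input is not described.

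**What to change.** Add one paragraph to the protocol and SAP, before fitting begins:

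1. The analysed separation for both conditions comes only from the laboratory model fitting, with the same bone model per subject. On-site and clinic-supplied values are not analysed.
2. The trial is chosen by rule, for example the first with all five stance points usable, and the frames are fixed before any fitting.
3. Each frame carries a random code that hides the condition, plus a bone-model code. The second code is needed because the models are subject-specific. Frames are cropped to the bone outline where possible.
4. Frames are fitted in random order across subjects and conditions, without access to the paired result.
5. All poses are locked before decoding. An existing team member who does not fit frames holds the code.
6. Frames with visible brace hardware are recorded. A sensitivity analysis without them is reported only if enough braced frames remain.

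If the fit is automated, say so and describe it.

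**Cost.** File preparation for at least 20 × 2 × 5 = 200 frames (240 if all 24 subjects are analysed) and one existing person to hold the code; no extra reader, imaging or subject procedure. The documents give no basis for a time estimate. Masking remains partial where hardware shows or where the shared bone model reveals which frames belong together.

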On the scheduled day of data collection, there will be at least two UT researchers present (which could also include the PI), as well as a study PI, (Drs. [name], [name]; [name], [name], [name], [name] [Sub-Investigators]) to conduct the fluoroscopic evaluation. Each subject will be asked to perform gait without the assistance of an offloading brace (Figure 1a). Then, each subject will be fitted with a Breg, off-the-shelf OA brace and will perform normal gait while under fluoroscopic surveillance (Figure 1b). To ensure each brace was fitted properly, Breg will be asked to send either a sales representative or an engineer to the evaluation site. Therefore, the sales representative or engineer will be asked to fit their brace on each of the subjects. This individual will sign a pledge of confidentiality.

[figure not shown]

Figure 1. Subject on a treadmill perform gait without a brace (a) and with a brace (b).

A Radiation Technician (RT) employed by Porter Adventist Hospital will perform the actual fluoroscopy procedure, following the subjects' OA knee with the unit as the activity is performed with and without the OA brace; only the knee joint (from the fluoroscopy machine) will be recorded on the fluoroscopy footage. The UT researchers, graduate research assistants (GRAs), which may include any of the following - [name], [name], [name], [name], [name] – will be present, although they will not perform the actual fluoroscopy procedure. They will be present during the fluoroscopy procedure to walk subjects through the activities, answer any questions that may arise, ensure data collection equipment is set up as needed and serve as consultants to the RT.

Any of these UT individuals, or study staff from Colorado Joint Replacement, will consent the participants. They will meet with each potential participant individually to make sure s/he has been properly informed of the procedures and to help with any of the IC form. CMR researchers will inform all subjects that they do not have to participate and are free to leave if they wish and will answer any questions subjects may have about the study. Participation is entirely voluntary.

Participants will be asked to practice the activity to ensure they can comfortably complete it and experience no pain with the fluoroscopy machine off (no radiation). The practice portion of the data collection without radiation will not be video-recorded.

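### The protocol lets clinic staff supply the unbraced separation value by an unstated method, which conflicts with its own plan to measure both conditions by study fluoroscopy

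*Protocol*

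**What the plan says.** The Private Health Information/Medical Record Data section of the protocol defines what is needed from each subject: "The only subject-specific data that will be necessary will be measurements of medial condyle separation", with and without a brace. It then treats the two conditions differently.

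- Braced: "Researchers will acquire the measurements with the brace while they are conducting the data collection". No other source is named.
- Unbraced: "Researchers may also acquire the subjects' medial condyle separation without the brace while they are present for data collection". Failing that, "if this is not possible or time does not permit, Colorado Joint Replacement staff may send that information to UT researchers".

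The provision returns later in the same section, in the paragraph on subject identifiers. There, "Colorado Joint Replacement staff may relate the measurements of medial condyle separation from the medial tibial plateau for each subject without a brace", with the stated triggers "time not permitting during data collection; researchers unable to collect measurement". Both places give the secure transfer route. Neither gives the imaging method, posture, point in the gait cycle, date or reader.

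The measurement text reads differently. Under Data Collection, Fluoroscopy, each subject walks first without and then with the brace, and the technician follows the knee "with the unit as the activity is performed with and without the OA brace". The model-fitting text in the JointVue three-dimensional ultrasound section takes stance-phase images in both conditions at five instants and compares the braced walk with the subject's own test without the brace. The SAP's Data Analysis section derives kinematics from fluoroscopic frames by 3D-to-2D registration. It mentions no other source.

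**The concern.** The unbraced value is half of the study's central comparison. When both values come from the same session, bone model and registration method, a measurement error common to both tends to cancel within the subject. If the unbraced value came from another method, any systematic difference between methods would sit on one side only. It could not be separated from the brace effect and, depending on its sign, could enlarge, shrink or imitate it.

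There is also a question of completeness. The comparison is planned at five stance instants, and nothing says whether a clinic value would exist at each of them.

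Finally, a reader cannot tell whether the unbraced fluoroscopic measurement is required, as the measurement text implies, or optional, as the privacy text says. The SAP has no rule for a value that arrives from outside the registered frames.

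**Working it through.** The documents give no expected effect, standard deviation, power or method offset, so there is no stated figure to reproduce. The check is a comparison of the texts, followed by conditional arithmetic.

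**Step 1. The texts side by side.**

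| Item | Fluoroscopy and model-fitting text; SAP | Private Health Information text |
|---|---|---|
| Braced value | Study fluoroscopy, registered | Researchers, at data collection |
| Unbraced value | Study fluoroscopy, registered | Researchers optionally; otherwise clinic staff |
| Stance instants | Five, both conditions (protocol) | Not stated for the clinic value |
| Method of clinic value | Not mentioned | Not stated |

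The conflict is confined to the unbraced row.

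**Step 2. Where could a clinic value come from?** The only clinic-side joint assessment described is a standing anteroposterior radiograph, in the protocol's opening summary. It is static and is not linked to this provision. The Clinical Observations section says that study data do not go back to the physician's office. No route is therefore described by which clinic staff would hold the registered fluoroscopic value. This makes a different method plausible but does not establish it.

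**Step 3. Consequence if a clinic value with an offset is used.** Let the effect be the mean over n subjects of braced minus unbraced. Suppose that m subjects have the clinic value as comparator, and let offset be the average of (clinic value minus registered value) in those m subjects. Each affected difference shifts by minus its own offset, so

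bias = -(m/n) x offset.

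The same expression applies to a difference between two condition means when the same n subjects contribute to both. Inputs: n = 20 (planned) or 24 (enrolled), from the protocol's opening summary. The values of m and the 1 mm offset are assumptions.

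| m | Size of bias per 1 mm offset, n = 20 | n = 24 |
|---|---|---|
| 0 | 0 | 0 |
| 1 | 1/20 = 0.05 mm | 1/24 = 0.04 mm |
| 2 | 2/20 = 0.10 mm | 2/24 = 0.08 mm |
| 4 | 4/20 = 0.20 mm | 4/24 = 0.17 mm |
| 10 | 10/20 = 0.50 mm | 10/24 = 0.42 mm |

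The protocol sets no limit on m.

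**Step 4. Cost of treating such subjects as missing.** Enrolling 24 for 20 leaves 24 - 20 = 4 losses, shared with ordinary dropouts. Below 20, with the same standard deviation, the standard error grows by sqrt(20/18) = 1.05 at 18 subjects and sqrt(20/16) = 1.12 at 16, that is by about 5% and 12%.

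**The case against.** The strongest reply is that all the text governing the analysis already uses one method. The protocol names the subject's own test without the brace as the comparator, both walks are filmed, and the SAP works only from registered frames. The disputed sentences sit in a section on access to records and secure transfer, and nothing there says that a transferred value replaces a registered one. The staff concerned may be study staff at the clinic, since the Fluoroscopy section uses that description, and the sentence about not returning data concerns clinical reading of images. An unspecified source is not the same as a different one. Use may also be rare: the unbraced walk comes first, and "Multiple trials of each activity may be conducted to ensure usable images have been acquired to complete the study".

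Most of this stands, and it limits the point. A reader might infer that the unbraced value will come from a standing radiograph, or that the comparison will mix methods. The documents say neither. A reader might also infer an inflated false-positive rate. That does not follow either: any such rate needs an invented number of affected subjects, an invented offset and a choice of test, and the SAP lists no paired test. No false-positive rate is claimed here.

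What the reply does not remove is the provision itself. It is stated twice, covers one condition only, and concerns the outcome measurement rather than background records. Its position in a privacy section does not stop it from authorising a second source.

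**Conclusion.** The concern holds as an internal conflict that should be resolved. The protocol permits an alternative source, of unstated method and timing, for the unbraced half of its central comparison. Its own measurement text and the SAP provide for study fluoroscopy only. Confidence is high that the provision exists and applies to the unbraced value alone, and moderate that a clinic value would come from a different method.

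The size is conditional: -(m/n) x offset in the mean difference, with m and the offset unknown and m possibly zero. The formula assumes that the clinic value is used as the comparator, that it refers to the same stance instant or summary as the braced value, that the offset is an average over affected subjects, and that the effect is expressed as a mean difference. It does not describe the rank test that the SAP would use for non-normal data. No threshold for a material bias is claimed.

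**What to change.** Reconcile the Private Health Information text with the Fluoroscopy and model-fitting text by removing the clinic-supplied value as a source for the comparison. State in both the protocol and the SAP that braced and unbraced separation come from same-session fluoroscopy, at the same five stance instants, with the same subject-specific bone model and registration method. Treat an unbraced recording that was not obtained as missing, and report the number and reasons.

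The change costs wording only. Its downside is that a few subjects may drop out of the comparison, with a small selection risk if recordings fail for reasons tied to gait or disease severity. The enrolment margin absorbs part of this loss.

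If the sponsor prefers to keep the clinic value, the second-best course is to name its method, say whether it covers all five instants, flag each affected subject, and repeat the analysis without them. That avoids the loss of subjects but leaves any offset in the main estimate.
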